6.0 Dose Delays/Modifications for Adverse Events

This study will use Common Terminology Criteria for Adverse Events v 4, which can be found at the CTEP, website: <http://ctep.cancer.gov/reporting/ctc.html>

Management of Anticipated Toxicities: Missed doses of radiation therapy and Sipuleucel -T will not be made up. Treatment should be stopped for any protocol treatment related Grade 3 toxicity or greater that cannot be controlled with good medical practice intervention. Treatment may be resumed upon resolution of that toxicity to Grade 2. A patient who experiences a Grade 3 or higher toxicity again will be removed from the study. There are no provisions for dose reductions of radiation therapy or Sipuleucel-T. The maximum delay in treatment will be 14 days. Patients who received at least one infusion of Sipuleucel-T

will not be replaced. Patients who received at least 50 % of anticipated dose of radiation therapy will not be replaced. Patients who received <50 % of anticipated dose of radiation therapy and / or who did not receive any infusions of Sipuleucel-T will be replaced.

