13.3 Statistical Analysis Plan

Primary Endpoint: Previous publications suggest 8% were unable or unwilling to receive all three infusions of Sipuleucel-T. We will stop accrual at any time if more than 2 patients are unable to receive all three infusions and more than 30% of the patients are unable to receive all three infusions. This rule has a 4% of stopping if 8% are unable or unwilling to receive all three infusions, and a 82% chance of stopping early if 33% are unable or unwilling to receive all three infusions (based on 1000 simulations). In addition, if 3 patients in the first 10 are unable to initiate Sipuleucel-T immunotherapy on Arm B, the study will hold accrual pending review by the COH DSMB, sponsor and PI. This slightly increase the chance of early stopping (3 of 10 is not "more than 30%" but equal to 30%). Previous publications suggest only 2% of patients are unwilling or unable to begin Sipuleucel-T immunotherapy.

In addition, to the above stopping boundaries, there will be a safety review of the toxicities after 10 patients have been treated on Arm B, or after any grade 3 or higher treatment related toxicity on Arm B. These rules are in place to limit patient exposure to arm B if it proves poorly tolerated or too toxic.

Secondary Endpoint:

From the IMPACT study, titers of antibodies against prostatic acid phosphatase exceeded 400 in 28.5% of the patients treated with Sipuleucel-T. By having a control group, a Fisher's exact test with a 0.200 one-sided significance level will have 86% power to detect the difference between non-radiation proportion, 0.285 and a radiation-treated group proportion of 0.570 when the sample size in each group is 25. Also, with 25 patients, if the true proportion about 400 is 28.5% in the control arm, and 48.5% in the radiation arm, there is less than a 5% chance (~1% if the radiation proportion is 57%) that the observed proportion will be higher in the control arm, and there is an 85% chance that difference will exceed 8% between the two arms. In addition, secondary endpoints will include measurements of immune responses to PA2024 and PSA and radiologic responses to therapy with Sipuleucel-T +/- external beam radiation therapy to single metastasis.

As a result, by having a concurrently randomized control arm, initial comparisons of Arm A and Arm B including the influence of radiation on PSA kinetics and response, toxicity and tolerability will help

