motivate future studies. For this exploratory secondary analysis, we will not include patients (if any) who do not start Sipuleucel-T immunotherapy, but will include all patients who start. A subset analysis of patients able to complete the planned three infusions will also be conducted.

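### Fisher's exact test leaves about a third of the accepted 0.200 error rate unused in the PAP antibody comparison and loses 4 to 6 points of power when the analysed arms are slightly unequal; Boschloo's test would avoid most of that loss

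*Combined protocol and SAP*

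**What the plan says.** Under Secondary Endpoint, section 13.3 takes its control rate from the earlier phase III trial, where "titers of antibodies against prostatic acid phosphatase exceeded 400 in 28.5% of the patients treated with Sipuleucel-T". It then states that "a Fisher's exact test with a 0.200 one-sided significance level will have 86% power to detect the difference" between that 0.285 and "a radiation-treated group proportion of 0.570 when the sample size in each group is 25". No other between-arm comparison in the plan has a stated power. The plan gives neither the test's attained false-positive rate nor its power at any other analysed size.

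Three other statements decide how many patients are analysed:

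- The end of section 13.3 calls the analysis exploratory and says "we will not include patients (if any) who do not start Sipuleucel-T immunotherapy"; everyone who starts is included. Under Primary Endpoint the section adds: "Previous publications suggest only 2% of patients are unwilling or unable to begin Sipuleucel-T immunotherapy".
- Section 6.0 says that "Patients who received at least one infusion of Sipuleucel-T" are not replaced, and that patients who had no infusion are replaced.
- Sections 13.2 and 4.4 give a 1:1 ratio and say who performs the randomisation, but not the method. Section 13.3 has no rule for a missing titre.

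**The concern.** Fisher's test conditions on the total number of responders. With about 25 patients per arm few p-values are attainable, so the largest one not above 0.200 can leave much of the allowance unused. The sponsor chose a liberal one-sided 0.200 because the comparison is meant to inform later studies. A test that runs at about two-thirds of that rate gives up some of the sensitivity the choice was meant to buy.

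The same discreteness makes power depend on the exact pair of analysed numbers. The printed figure applies to 25 per arm. If one arm ends a patient or two short, the rejection region shifts and power drops by more than the lost patients alone would explain. A real effect of radiation on the antibody response would then be missed somewhat more often than the plan suggests.

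**Working it through.** **Inputs, all from section 13.3:** control rate 0.285; radiation rate 0.570, with 0.485 as the plan's second scenario; 25 per arm; one-sided 0.200.

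**Fisher.** For a responders of n1 controls and b of n2 radiation patients, the one-sided p-value is the sum over j ≥ b of C(n2, j)·C(n1, a+b−j) / C(n1+n2, a+b). Reject if p ≤ 0.200. Power is the sum, over all rejected (a, b), of Bin(a; n1, 0.285)·Bin(b; n2, 0.570). The false-positive rate uses the same region with one common rate in both arms.

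**The plan's figure.** With 25 per arm, power = 0.8601. The stated 86% reproduces.

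**Attained false-positive rate, 25 per arm.** 0.136 at a common rate of 0.285; maximum 0.161, at 0.50. So 0.136/0.200 = 68% of the allowance is used at the planning rate.

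**Boschloo.** Use the Fisher p-value as the statistic and reject if it is at most c. Here c is the largest attainable value for which the false-positive rate, maximised over all common rates, stays at or below 0.200. With 25 per arm c = 0.269 and the maximum is 0.197. Example: 6 control and 9 radiation responders of 25 each give Fisher p = 0.269 (not rejected) and Boschloo p = 0.197 (rejected). At every size checked c was at least as large as Fisher's cut-off, so Boschloo rejects whenever Fisher does.

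**Results at 28.5% v 57%** (false-positive rate at a common 28.5%)

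| Control / radiation | Fisher power | Boschloo power | Gain (points) | Fisher false-positive | Boschloo false-positive | Boschloo maximum |
|---|---|---|---|---|---|---|
| 25 / 25 | 86.0% | 86.4% | 0.4 | 0.136 | 0.194 | 0.197 |
| 24 / 24 | 84.6% | 85.2% | 0.6 | 0.131 | 0.194 | 0.195 |
| 23 / 23 | 83.0% | 84.0% | 1.0 | 0.126 | 0.193 | 0.193 |
| 25 / 24 | 82.2% | 88.9% | 6.6 | 0.117 | 0.189 | 0.199 |
| 24 / 25 | 81.4% | 88.0% | 6.6 | 0.130 | 0.177 | 0.199 |
| 25 / 23 | 80.0% | 85.7% | 5.7 | 0.117 | 0.163 | 0.192 |

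Over all twelve unequal pairs with 22 to 25 per arm, the gain runs from 3.2 points (24/22: 81.2% to 84.4%) to 7.9 points (23/22: 78.5% to 86.3%). Over all sixteen pairs, equal and unequal, the false-positive rate at 28.5% is 0.108 to 0.139 for Fisher and 0.148 to 0.194 for Boschloo.

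**At 28.5% v 48.5%.** Fisher 67.4% and Boschloo 69.3% at 25/25; 62.3% and 72.9% at 25/24; 61.1% and 70.8% at 24/25.

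**Random missing titres.** The documents give no rate, so a range is assumed. If each of 25 patients per arm independently lacks a titre with probability 2%, 5% or 8%, average Fisher power is 83.5%, 81.8% or 80.6%, and average Boschloo power is 87.1%, 86.5% or 85.7%.

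**Choice of unconditional test.** Ordering outcomes by the pooled Z statistic instead gains only 0.3 points at 25/24 and 3.4 points at 24/25, so the plan would have to name the test.

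**The case against.** The strongest reply is that nothing is wrong. The printed power is exact, already includes Fisher's conservatism, and says openly that it applies "when the sample size in each group is 25". An alpha of 0.200 is a limit, not a quota, and with so liberal a limit a conservative test is defensible. The analysis is exploratory and no decision depends on crossing 0.200. All of this stands, and it is why the point is optional.

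A reader might infer more than the documents support:

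- **That the 2% who do not start shrink the arms.** Section 6.0 replaces patients with no infusion, so section 13.3's exclusion and that replacement together aim at 25 starters per arm. Section 6.0 is unclear for an Arm B patient with at least half the radiation and no infusion, and it does not say that a replacement joins the same arm, but neither gap makes unreplaced non-starters the expected case.
- **That the plan's 8% is a missing-titre rate.** It is the share not receiving all three infusions, and section 13.3 keeps those patients in the analysis if they start.
- **That 86% collapses at any size other than 25 per arm.** At 24/24 it is still 84.6%; the larger drop comes from unequal arms.
- **That the switch gains several points at the planned size, at no cost.** At 25/25 it gains 0.4 points, while the actual false-positive rate at 28.5% rises from 0.136 to 0.194.
- **That the control arm exists only for this test.** Section 13.3 also wants it for PSA, toxicity and tolerability comparisons.

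What remains is that equal analysed numbers are not assured. The Study Calendar takes immune samples before study, at week 4 and from week 12; by the study schema, week 4 (Day 22) is the day of the first infusion. Under section 5.3 follow-up ends at progression that requires further therapy. A starter who leaves before week 12 may therefore have no useful post-treatment titre, and is not replaced. No blocking is stated either.

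**Conclusion.** The 86% is right for 25 per arm and needs no correction. The point that holds is about efficiency and robustness. At the planning rate Fisher's test uses 0.136 of the accepted 0.200, and with one arm one or two patients short its power is 80.0% to 82.2% at the three unequal sizes tabulated. Boschloo's test holds 85.7% to 88.9% at those sizes. The gain is about 3 to 8 points across unequal arms of 22 to 25, and at most about 1 point when the arms are equal at 23 to 25.

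This rests on the plan's own rates and on the assumption that missing titres or allocation leave the analysed arms slightly unequal. The documents make that possible but do not quantify it. If exactly 25 and 25 are analysed, the choice of test hardly affects power. It is a low-cost, optional improvement to an exploratory secondary comparison.

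**What to change.** In section 13.3, name Boschloo's exact unconditional test, one-sided at 0.200, for the between-arm comparison of the proportion with a PAP titre above 400. Restate the power at 28.5% v 57% as 86.4% with 25 per arm and about 86% to 89% with one arm one or two patients short.

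If Fisher's test is kept, leave the 86% and add that the actual false-positive rate at 28.5% is about 0.11 to 0.14 with 22 to 25 analysed per arm, and that power is 80.0% to 82.2% at 25/24, 24/25 and 25/23.

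The change costs one sentence and needs no extra patients, visits or data; the test is in standard software. Its real price is the higher actual false-positive rate at 28.5%, about 0.15 to 0.19, which stays within the limit the plan already accepts.

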13.2 Sample Size Accrual Rate

Patients with metastatic castration-resistant prostate cancer who are candidates for Sipuleucel-T immunotherapy. Total Sample size 50. Anticipated accrual is 2-3 patients a month. Likely duration of the study is 2 years. Randomization is 1:1.

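### With 25 per arm, 85% is the chance of a difference of at least 8%; the chance that it exceeds 8% is 77%

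*Combined protocol and SAP*

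**What the plan says.** Section 13.2 sets the size and allocation: "Total Sample size 50" and "Randomization is 1:1". Section 13.3, under the secondary endpoint, gives the power of Fisher's exact test for 28.5% versus 57.0% "when the sample size in each group is 25". It then adds two descriptive properties of the observed difference, taking the true proportions above a titer of 400 to be 28.5% (control) and 48.5% (radiation):

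- a reversal, with control showing the larger observed proportion, is put below 5%, or near 1% should the radiation figure be 57%;
- on the size of the difference, "there is an 85% chance that difference will exceed 8% between the two arms".

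No other section defines how "exceed" is to be read or gives a different denominator for this calculation.

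**The concern.** The observed difference between two arms of 25 can only be a multiple of 1/25, that is, of 4 points. The threshold of 8% falls exactly on one of those values, so "more than 8%" (three or more patients) and "at least 8%" (two or more) are different events. The plan is alert to this elsewhere: in the stopping-rule paragraph of the same section it points out that three of ten equals 30% and does not exceed it.

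A reader who takes the sentence literally would put the chance of not seeing a difference above 8% at 15%. If the true figure is 77%, that chance is 23%. What is at stake is the accuracy of a stated operating characteristic for the immune-response comparison, which the plan says will help motivate later studies. No decision rule in the plan uses the 8% threshold.

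**Working it through.** **Inputs (sections 13.2 and 13.3).** n = 25 per arm; control proportion 0.285; radiation proportion 0.485; threshold 8% = 2/25; stated probability 85%.

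**Method.** Let C ~ Bin(25, 0.285) and R ~ Bin(25, 0.485), independent. The observed difference is (R − C)/25, and

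P(R − C ≥ k) = Σ P(C = i) · P(R = j) over all i, j with j − i ≥ k.

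The sum is evaluated exactly over all 26 × 26 outcomes.

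**Does the method reproduce the plan's neighbouring figures?**

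| Quantity | Stated | Exact |
|---|---|---|
| Fisher power, one-sided 0.20, 0.285 vs 0.570 | 86% | 86.0% |
| P(control observed higher), radiation 0.57 | about 1% | 1.26% |
| P(control observed higher), radiation 0.485 | less than 5% | 5.22% |

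The first two agree. The third is just above the stated bound; it reaches 5% when the radiation proportion is about 0.488.

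**The 8% statement, 0.285 vs 0.485.**

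| Event | Patients | Exact probability |
|---|---|---|
| Difference at least 8% | R − C ≥ 2 | 0.8507 |
| Difference exactly 8% | R − C = 2 | 0.0785 |
| Difference exceeds 8% | R − C ≥ 3 | 0.7723 |

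The probability of landing exactly on 8% accounts for the whole gap: 0.8507 − 0.7723 = 0.0784, which agrees with 0.0785 up to rounding. The chance of a difference of 8% or less is 1 − 0.7723 = 0.2277, against the 0.15 implied by the text.

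**Other readings of "exceed 8%" at 25 per arm.**

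| Reading | Probability |
|---|---|
| Absolute difference above 8% | 0.786 |
| Absolute difference at least 8% | 0.878 |
| Normal approximation, no continuity correction | 0.814 |
| Normal approximation, continuity-corrected, above 8% | 0.771 |
| Unrounded computer comparison of j/25 − i/25 with 0.08 | 0.824 |
| Radiation proportion 0.57, above 8% | 0.915 |

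None gives 85%. With control fixed at 0.285, the chance of exceeding 8% reaches 85% only when the radiation proportion is about 0.525, whereas the text says 0.485. The continuity-corrected normal approximation for "at least 8%" gives 0.851, in line with the exact 0.8507.

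**The case against.** The arithmetic is not in dispute; the objections concern weight and framing.

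- *No decision rests on it.* The 8% is not a success margin, a boundary or a test criterion, and the plan calls the comparison exploratory. This stands, and it keeps the point minor.
- *The gap is a boundary effect at one denominator.* A difference of exactly 8% cannot occur with 24 versus 24, where both readings give 84.2%, close to the stated 85%. Likewise both readings give 83.2% with 24 control and 26 radiation patients, 81.8% with 25 and 24, and 79.9% with 24 and 25. The secondary analysis drops patients who never start Sipuleucel-T, and section 4.4 gives no method that guarantees 25 and 25. This is a fair limit on the size of the discrepancy. But the sentence itself is stated for 25 patients, and section 6.0 replaces patients who receive no infusion, so 25 per arm is the right basis for checking it.
- *The intended word is not known.* The close match to 85% makes it likely that "at least" was calculated, but does not prove it. Keeping "exceed" and changing the figure to 77% would be equally correct. This stands, and giving both figures settles it.
- *Simulation error.* Section 13.3 reports 1000 simulations for the stopping rule. If the same number was used here (an assumption), the standard error at 85% would be about 1.1 points, √(0.85 × 0.15/1000), far short of a gap of nearly 8. For the 5% figure it would be about 0.7 points, so 5.2% could not be told apart from 5%. That item is therefore no more than rounding.

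**Conclusion.** The statement is wrong as worded. At 25 per arm and true proportions of 28.5% and 48.5%, the chance that the observed difference exceeds 8% is 77.2%, about 8 points below the stated 85%; the stated figure is the chance of a difference of at least 8% (85.1%). The result assumes exactly 25 evaluable patients per arm, independent binomial outcomes, and a difference taken as radiation minus control, all of which follow the plan's own description. The less-than-5% figure is 5.2%, a slip at the level of rounding. The importance is low: the sample size, primary endpoint, stopping rules, Fisher power and the roughly 1% figure at 57% are unaffected.

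**What to change.** Reword the sentence in section 13.3 so that word and number agree. The simplest form gives both figures: an 85% chance that the difference will be at least 8%, and a 77% chance that it will exceed 8%. Keeping "exceed" and replacing 85% with 77% is equally acceptable. In the same sentence, replace the less-than-5% wording with about a 5% chance that the observed proportion is higher in the control arm.

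As optional context, not needed to correct the error, the plan could add how often such differences arise with no true effect. With 28.5% in both arms, a difference of at least 8% in favor of radiation occurs 32% of the time, and one above 8% occurs 22% of the time.

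The cost is two wording changes in one sentence, with no change to the sample size, tests or rules.

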Eligible patients will meet the standard criteria for approved use of Sipuleucel -T. Patients will be randomized to receive standard Sipuleucel-T regimen (Arm A) or Sipuleucel-T preceded by radiation therapy to single site of metastatic disease (Arm B). In patients assigned to Arm B one metastatic site will be selected for radiation based primarily on the safety of radiation in that location. Radiation to bone metastases from L3 down to pelvis and femurs will be excluded provided that patients have other areas of metastases. Patients who have metastases only in the above locations (L3 down to pelvis and femurs) will be allowed provided that they have normal WBC and they will not receive radiation to more than 20% of the bone marrow. Patients will be treated with 300 cGy/day to 3000 cGy. Approximately 7 days after completion of radiation therapy patients will begin therapy with Sipuleucel-T autologous vaccine.
Endpoints:

Primary Endpoint:
 
The primary endpoint in this trial will be percent of patients able to receive all three infusions of Sipuleucel-T following radiation therapy. This endpoint reflects both tolerability and the ability to collect adequate numbers of CD54+ cells for the generation of Sipuleucel-T.
 
Secondary Endpoint:
 
Secondary endpoints will include measurements of immune responses to PAP, PA2024 and PSA and radiologic responses to therapy with Sipuleucel-T +/- external beam radiation therapy to single metastasis. Toxicity comparison between the two arms is also a secondary endpoint.

Sample Size:
Total Sample size is 50 randomized in a 1:1 fashion to Arm A and B. Anticipated accrual is 2-3 patients a month.
Estimated Duration of the Study
24 months
Summary of Subject Eligibility Criteria:

Inclusion Criteria:
 
Patients with metastatic castration-resistant prostate cancer who are candidates for Sipuleucel-T immunotherapy. Metastatic, minimally symptomatic or asymptomatic disease, ECOG PS 0-2
 
Exclusion Criteria:
 
Liver metastases, known brain metastases, > 2 prior chemotherapy regimens

Investigational Product Dosage and Administration:
Not Applicable. Radiation therapy constitutes investigational component of this study

Clinical Observations and Tests to be Performed:

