5.0 Treatment Program

5.1 Treatment Overview

Treatment will be performed on an outpatient basis. Patients randomized to Arm A will be treated with standard Sipuleucel - T. Leukapheresis will be performed at the contracted, designated Dendreon facility and Sipuleucel-T infusion will be performed at the City of Hope infusion clinic approximately 72 hours after leukapheresis. This process will be repeated every 2 weeks times three. Patients randomized to Arm B will undergo 2 weeks of radiation therapy to single metastatic site followed by 7 days of rest followed by treatment with Sipuleucel- T on an identical schedule as Arm A (see study schema) Delays in leukapheresis of up to 2 weeks for each cycle are acceptable regardless of cause.

For a tabular view of the treatment, monitoring, and follow-up schedule, see study calendar in Section 10.

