8.2 Radiation therapy

8.2.1 Treatment Plan:

In patients assigned to Arm B one metastatic site will be selected for radiation based primarily on the safety of radiation in that location. Radiation to bone metastases in L3-S5, pelvis and femurs will be excluded provided that patients have other areas of metastases. Patients who have metastases only in the above locations (L3-S5, pelvis and femurs) will be allowed provided that they have normal WBC and they will not receive radiation to more than 20% of the bone marrow. The gross tumor volume (GTV) will be defined as the radiological dimensions of the lesion as identified by CT and/or MRI. The planning tumor volume (PTV) is defined as the GTV plus 1 cm. For lesions that move with respiration (Rib and lung parenchymal lesions for example) CT simulation will be performed at inspiration and expiration to define lesion position during the respiratory cycle. The GTV will be defined based on lesion position during the respiratory cycle. Radiation treatment fields will be arranged to minimize dose to the marrow and whole body. Conventional AP/PA technique will be used. Field will be limited to 10 by 10 cm. Patients will be treated with 300 cGy/day to 3000 cGy; Approximately 7 days after completion of radiation therapy, patients will begin therapy with Sipuleucel-T autologous vaccine.

8.2.2 Toxicity:

The risks of radiation therapy depend on the part of the body being treated. These side effects are generally mild and expected to resolve 1-2 weeks after radiation is completed:

- fatigue,
- anorexia
- gastroesophageal reflux
- diarrhea
- nausea
- dysuria
- urinary frequency
- pain flare
- skin rash,
- neutropenia,
- thrombocytopenia,
- anemia

Long term effects of radiation also depend on the specific location being treated and include:

- pneumonitis
- cystitis
- hematuria
- secondary malignancy
- chronic diarrhea
- bowel perforation

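### As written, the exploratory between-arm toxicity and tolerability comparison covers only patients who start Sipuleucel-T, so it omits Arm B patients stopped by radiation effects (minor)

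*Combined protocol and SAP*

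**What the plan says.** The synopsis, under Endpoints, states: "Toxicity comparison between the two arms is also a secondary endpoint". Section 13.3 describes initial comparisons of the two arms "including the influence of radiation on PSA kinetics and response, toxicity and tolerability". The next sentence sets the population for this exploratory secondary analysis: "we will not include patients (if any) who do not start Sipuleucel-T immunotherapy", while everyone who starts is included. A subset analysis of patients who complete three infusions is added. No other analysis set for toxicity appears in the document.

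Section 5.1 gives Arm B two weeks of radiation and 7 days of rest, then Sipuleucel-T on the same schedule as Arm A. The schema puts the first collection on Day 19 and the first infusion on Day 22. On how many patients fail to start, Section 13.3 says: "Previous publications suggest only 2% of patients are unwilling or unable to begin Sipuleucel-T immunotherapy".

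**The concern.** Membership of the analysis set is decided after randomisation, and only in Arm B can radiation influence it. Both arms can lose patients before the start of Sipuleucel-T, but only Arm B patients have by then been given a treatment whose toxicity is the question.

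The protocol itself shows how this could happen. Section 8.2.2 lists neutropenia, thrombocytopenia and anaemia among radiation effects. Section 6.0 stops treatment for related toxicity of grade 3 or higher that cannot be controlled. Section 5.2.2 removes patients whose treatment is delayed by more than two weeks because of adverse events. Section 13.3 has an accrual hold specifically for Arm B patients who cannot begin Sipuleucel-T.

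At stake is the accuracy of an exploratory comparison. It has no decision rule, but its stated purpose is to inform later studies of the combination.

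**Working it through.** The plan gives no figure for the toxicity comparison, so there is none to reproduce. The two calculations that Section 13.3 does give were checked. Exact Fisher power is 86.0% (stated 86%). The stopping probabilities are 3.6% and 82.4% (stated 4% and 82%). None of these bears on this point.

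**1. Who is excluded.** Sections 5.1 and 13.3 together give the order randomisation, radiation (Arm B only), rest, start of Sipuleucel-T, entry to the analysis set. Section 13.3 does not say whether starting means the first collection or the first infusion. Under either reading, radiation comes before it.

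**2. How many.** Inputs: 25 per arm (50 patients, 1:1, Section 13.2) and a 2% non-start rate (Section 13.3, from Sipuleucel-T publications).
- Expected Arm B exclusions = 25 × 0.02 = 0.5.
- P(at least one) = 1 − 0.98^25 = 39.7%.

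The documents give no non-start rate after radiation, so 1, 2 and 3 of 25 are used below as assumptions.

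**3. Adverse events.** Let b be the grade 3-5 rate among starters, d the share excluded and s the share of excluded patients with such an event. The rate in the whole arm is d·s + (1 − d)·b, so the shift from the reported b is d·(s − b). For illustration b = 186/601 = 30.9% (Section 8.1.6, Table 1). The values of s are assumed.

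| Excluded of 25 | d | s = 0 | s = 0.5 | s = 1 | Shift (points) |
|---|---|---|---|---|---|
| 0.5 (documents' rate) | 2% | 30.3% | 31.3% | 32.3% | −0.6 to +1.4 |
| 1 (assumed) | 4% | 29.7% | 31.7% | 33.7% | −1.2 to +2.8 |
| 2 (assumed) | 8% | 28.5% | 32.5% | 36.5% | −2.5 to +5.5 |
| 3 (assumed) | 12% | 27.2% | 33.2% | 39.2% | −3.7 to +8.3 |

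Arm B is understated only if s exceeds b, that is, if more than 30.9% of excluded patients had an event.

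For scale, the standard error of one arm's rate is √(0.309 × 0.691 / 25) = 9.2 points. That of the difference between arms is √(2 × 0.309 × 0.691 / 25) = 13.1 points.

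**4. Completion of three infusions.** With k non-starters and c starters who do not complete, non-completion is (c + k)/25 in all randomised patients and c/(25 − k) in starters. The difference is k(25 − k − c) / [25(25 − k)], which is never negative. With c = 2 (assumed):
- k = 1: 12.0% against 8.3%.
- k = 2: 16.0% against 8.7%.
- k = 3: 20.0% against 9.1%.

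The same formula applies to Arm A, so the gap between arms is distorted to the extent that non-starting is more common in Arm B.

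**5. Does the hold limit this?** It needs 3 non-starters among the first 10 Arm B patients. The chance of that is 7.0% at an assumed 10% non-start rate and 32.2% at 20%. It would often leave such exclusions in place.

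**The case against.** The best counter-argument is that stopping before Sipuleucel-T is already handled where it matters. The primary endpoint is receipt of all three infusions after radiation. Section 13.3 adds the hold and a safety review after 10 Arm B patients or any related event of grade 3 or higher on that arm. This stands as a limit on the consequence. A reader might infer that Arm B non-starters go unmonitored or that the feasibility result is biased, and the documents do not support that. These provisions do not, however, return the patients to the between-arm comparison.

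Second, numbers may be low. Section 5.1 says: "Delays in leukapheresis of up to 2 weeks for each cycle are acceptable regardless of cause". Section 8.2.2 calls the short-term radiation effects "generally mild and expected to resolve 1-2 weeks after radiation is completed". This also stands, and is a reason to rate the point minor.

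Third, the exclusion sentence sits in a section mainly about antibody titres, and toxicity is listed elsewhere as an objective and endpoint with no such limit. The scope is therefore the natural reading rather than an explicit statement. With no other set defined, an analyst following the plan would still apply it.

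Fourth, a reader might infer that events before Sipuleucel-T are not recorded, because scheduled adverse-event evaluation begins at week 4. That goes too far. Section 7.5 requires serious events from consent, and the Section 10.0 calendar has blood counts in weeks 1 to 3. The gap lies mainly in the analysis set.

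Finally, Section 6.0 might seem to settle whether such patients count. It says "Patients who received at least 50 % of anticipated dose of radiation therapy will not be replaced", and then that those "who did not receive any infusions of Sipuleucel-T will be replaced". The two sentences conflict for a patient with at least half the radiation dose and no infusion. Section 13.3 excludes that patient from the comparison in either case, so the conflict is a separate matter.

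**Conclusion.** The point holds, at minor severity. On its natural reading, Section 13.3 removes from the exploratory toxicity and tolerability comparison those Arm B patients whom radiation stopped before Sipuleucel-T.

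For completion of three infusions the direction is fixed: leaving out non-starters can only understate Arm B non-completion. For adverse events it is tempting to say that Arm B toxicity must be understated, but the documents do not establish that. It is likely when radiation effects are the reason for stopping. Patients who were merely unwilling, and who never had an infusion, could have fewer events than starters.

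The size is unknown and probably small: −0.6 to +1.4 points at the documents' 2% rate, and at most 8.3 points with 3 of 25 excluded, less than the 9.2-point standard error of one arm. These figures rest on a borrowed 30.9% base rate from Sipuleucel-T trials and on assumed exclusion counts and event shares. No decision rule in the trial changes.

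**What to change.** In Section 13.3:
- Compare toxicity by randomised arm in all randomised patients who received any protocol treatment, meaning at least one radiation fraction or one leukapheresis, whether or not they start Sipuleucel-T or are later replaced.
- Compare completion of three infusions in all randomised patients.
- Show events before the first Sipuleucel-T collection separately from later ones, using data already captured: serious events from consent, the week 1 to 3 blood counts, and adverse events at existing visits.
- Keep the starters-only set for the immune, PSA and radiologic analyses.

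The cost is a few sentences and no extra visits. The Arm B rate may look less favourable.

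Early events will not be ascertained equally, and this should be stated with the result. Arm A joins the calendar at week 3, so its week 4 evaluation (Day 22) comes 3 days after first collection (Day 19). In Arm B the same evaluation comes about three weeks after radiation begins, and only Arm B has blood counts in weeks 1 and 2.

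Separately, the two replacement sentences in Section 6.0 must be reconciled.
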